## Delay of ARHL in patients taking

*CCBs.* In our preliminary study, a total of 35 white female patients have completed their first visit, with 26 of them using amlodipine (74%) for

more than one year. We compared this CCB group with two control cohorts, also of white females: control 1 group

**Fig. 1. CCB protection against ARHL.** Participants taking CCBs show better hearing thresholds than participants taking no CCBs even at low frequency regions (0.25 to 1 kHz).

able L. Least Squares Means with Bonferroni Correction Model 1			
		Vs. Control 1	Vs. Control 2
Cohort	LS Mean	p-value	p-value
CCB	19.77	1.0000	.9202
Control 1	20.28		.0784
Control 2	17.50		

(Con 1) from the Rochester, NY, area (447 participants) and control 2 group (Con 2) from the St. Louis, MO, area (55 participants) (**Fig. 1**).

Since ARHL starts at higher frequencies in the cochlea, we divided audiograms into three pure tone averages (PTA): averages of 0.25, 0.5, and 1 kHz (PTAL); averages

of 2 and 4 kHz (PTAH24); and averages of 2, 4, and 8 kHz (PTAH248). The means for the CCB group were: PTAL (15.1 dB HL), PTAH24 (20.7 dB HL), and PTAH248 (24.0 dB HL), and the means for the control 1 group were: PTAL (20.1 dB HL),

Гa	ble 2. Least S	qua res means	with Bonferroni	Correction Model 2
			Vs. Control 1	Vs. Control 2
	Cohort	LS Mean	p-value	p-value
	CCB	28.17	.0420*	1.0000
	Control 1	35.19		.11
	Control 2	28.54		

Table 3. Least Squares Means with Bonferroni Correction Model 3

		Vs. Control 1
Cohort	LS Mean	p-value
CCB	32.41	.0145*
Control 1	39.28	

PTAH24 (30.7 dB HL), and PTAH248 (35.2 dB HL). Since there were no data for 8 kHz for the control 2 group, the means for this group were PTAL (20.7, dB HL) and PTAH24 (29.3 dB HL). The two-tailed unequal variance t-test showed a significant difference between the CCB and the control 1 group for PTAL (p = 0.00067), PTAH24 (p = 0.00001), and PTAH248 (p = 0.00021), and a significant difference between the CCB and control 2 groups for PTAL (p = 0.02777) and PTAH24 (p = 0.00959). To correct for possible influences from both age and the three cohort sites, we used multivariate regression models with the Bonferroni correction method (**Table 1**, **2** and **3** for PTAL, PTAH24 and PTAH248, respectively). No significant difference was observed for PTAL between the CCB and control 1 or 2 groups (**Table 1**), or PTAH24 (**Table 2**) between the CCB and

control 2 group. However, statistically significant differences were found for both PTAH24 and PTAH248 between the CCB and control 1 group (**Table 2** and **3**). These data indicate CCB had beneficial effects against peripheral ARHL.

## 1.5 NIHL and Drilling Noise During Skull-based Surgery

Patients undergoing skull-based surgery are unavoidably exposed to noise from operative drills. High-speed drills that are capable of producing elevated levels are used during skull based surgeries (Hilmi et al., 2011; Yu et al., 2014). Hilmi et al. (2011) used accelerometers with cadaver temporal bones to measure the bone-transmitted drill noise. The authors found that the while the highest overall bone-conducted noise levels occurred while drilling on the mastoid process with a sound level of 110.2 dBA, other drilling locations such as the cranial base produce excessive amounts of drill noise primarily in the 2-4 Hz bandwidth. If bone-transmitted surgical drilling noise exposure was regulated by occupational safety organizations such as the National Institute of Occupational Safety and Health (NIOSH), the exposure time duration would be limited to between 1.5 to 12 minutes depending on drill location.

The drilling noise transmitted to the unoperated ear through the skull is difficult to prevent. Thus, noise-induced damage cannot be avoided by mechanical protection such as ear plug. Many patients who undergo a skull-based surgery for treatment to an affected ear, have normal or near-normal hearing in the contralateral ear. Therefore, the unoperated, normal-hearing ear is subjected to a similar drill-noise intensity compared to the operated side (Tos et al., 1984; Hickey and O'Connor, 1991). It is not surprising that temporary cochlear changes are commonly observed in unoperated ears. It has been shown that surgical drilling may have a temporary effect on the amplitude of the otoacoustic emissions of the ear contralateral to the surgical site (Baradaranfar et al., 2015; Shenoy et al., 2015). Furthermore, it has been reported that the incidence of a permanent SNHL (PTS) following tympanomastoid surgery is between 1.2% and 4.5% (Tos et al., 1984). PTS is also observed in some studies (Palva and Sorri, 1979; Lustig et al., 1995; Hallmo and Mair, 1996; Goyal et al., 2013; Abtahi et al., 2016).

The overarching goal of this study is to test whether ZNS can prevent temporary cochlear changes and PTS in patients undergoing skull-based surgery. Participants will be randomized to receive either active treatment (ZNS) or placebo.

#### 2.0 STUDY OBJECTIVES

#### 2.1 Primary Objective

To determine if preoperative and/or postoperative ZNS is more effective than placebo at preventing PTS in the contralateral ear of patients undergoing drilling during skull base surgery.

## 2.2 Secondary Objectives

To determine if preoperative ZNS is more effective than placebo at preventing temporary changes in cochlear health, synaptopathy, and degraded speech perception in the contralateral ear of patients undergoing drilling during skull base surgery.

To identify a genetic risk profile associated with drilling-induced hearing loss we will survey known genetic markers associated with NIHL including markers in CDH23, PCDH15, EYA4, MYO1A, KCNMA1 and OTOG (Zhang et al., (2019) and zonisamide (ZNS) metabolism, CYP2C9 and CYP2C19 (Saruwatari et al., 2010). If significant associations are observed and validated in a subsequent clinical study, we will optimize drug dosages based on a subject's genetic profile.

#### 3.0 ELIGIBILITY CRITERIA

#### 3.1 Inclusion Criteria

- 1. Patients who are scheduled to undergo a skull-based surgery that requires at least 45 minutes of surgical-drilling.
- 2. At least 18 years of age.
- 3. Air conduction thresholds in the non-operated ears are to be no worse than 25 dB HL for pure tone average 0.5, 1, and 2 kHz with no individual threshold greater than 30 dB HL, and no worse than 45 dB HL at 4 kHz at screening.
- 4. Observed air-bone gap  $\leq$  10 dB HL at 0.5, 1, 2, and 4 kHz, with normal tympanometry.
- 5. Ability to understand and willingness to sign an IRB approved written informed consent document.

#### 3.2 Exclusion Criteria

- 1. History of known sulfa allergy or hypersensitivity to carbonic anhydrase inhibitors.
- 2. History of moderate-to-severe kidney or liver disease.
- 3. Acute viral, bacterial, fungal or parasitic infection.

- 4. History of seizures.
- 5. Currently pregnant or breast-feeding.
- 6. Any current or history of ear disorder and/or central auditory dysfunction in the non-operated ear.
- 7. History of ototoxic drug use.
- 8. Current use of strong/moderate 3A4 inhibitor/inducer and grapefruit juice.

Note: For secondary outcomes analysis only, exclusion criteria is as follows:

- a) DPOAE data will be used as a secondary outcome measure, and participants will be excluded if their DPOAE is absent at more than 4/10 frequencies. Criteria for a present response is any response that is > 5 dB SPL above the noise floor and replicable within ±5 dB SPL.
- b) ECochG: Participants will be excluded if the ECochG/ABR wave I response is absent.
- c) WIN test: Participants with WIN scores greater than moderate difficulty or 14.9 dB SNR will be excluded.

Participants will not be excluded from the study for not meeting secondary outcome criteria.

#### 3.3 Inclusion of Women and Minorities

Both men and women and members of all races and ethnic groups are eligible for this trial.

#### 4.0 STUDY DESIGN

This study is a randomized, double-blinded placebo-control trial with three parallel groups, to make use of a common control group. Subjects will be randomized in a balanced fashion into one of 3 arms: ZNS 100 mg pre-op, Placebo, or ZNS 100 mg post-op.

The primary efficacy endpoint will be the proportion of PTS-positive subjects defined as the ratio of PTS-positive subjects to total number of subjects within each study arm/group. Subjects defined as PTS-positive will demonstrate an increase in threshold that is ≥10 dB HL at any frequency from 2-6 kHz post-surgery as compared to baseline audiogram.

The secondary efficacy outcome measures will be: (1) the proportion of PTS-positive subjects as defined above, but the definition of PTS will also include the NIOSH red

flag guideline for permanent threshold shift: an increase in hearing threshold level of 15 dB or more at any frequency (2, 3, 4, 6 kHz). (2) The rate of temporary cochlear change as measured by a DPOAE amplitude shift at any frequency that is significantly greater than the stability of each measurement (i.e., 95% confidence interval of each measurement do not overlap). The rate of DPOAE shift is the ratio of DPOAE shift-positive subjects to total subjects within each arm.

To ensure double-blinding of the trial, each subject will be randomized to one of three treatment arms via an interactive randomization tool (IRT) and assigned to study group. Once randomized, each subject will be provided a kit on the day of surgery that contains two bottles, with one package labeled to be taken prior to surgery and another package designated to be taken within 12 hours after surgery or when the patient is released clinically to oral medication. For subjects randomized to "ZNS pre-op", the pre-op package will contain one ZNS capsule (100 mg PO) and the post-op package will contain one placebo capsule that looks, smells, and tastes the same as ZNS capsules. For subjects randomized to "ZNS post-op", the pre-op package will contain one placebo capsule and the post-op package will contain one ZNS capsule (100 mg PO). For the subjects randomized to "placebo", both pre- and post-op packages will contain placebo.

The study will be "masked" or "blinded" in the sense that all the study participants and the study team members will be blinded to the assignment in the study groups. Only the pharmacist who will prepare the study drug kits and the unblinded Statistician will have access to the kit assignments. A copy of the randomization kit list with study ID assignments will be saved in a limited access folder on a secure network server at Pharm-Olam. The Medical Monitor will be contacted in emergent medical cases when knowing the treatments assignment is mandatory for clinical care of the patient.

At the time when we will need to "freeze" the data sets for purposes of developing the DSMB report, a series of SAS programs will be run from an independent programmer to produce data for each pairwise comparison into two subsets of data from the total cohort. Each subset will be de-identified. A previously prepared SAS code will be run in each subset and the output will be used to complete the table shells where the groups will not be identified. The programmer preparing subsets will not be involved in the handling of data forms or the analysis of data.

Study participants will be recruited from the Washington University Otology clinics. Patients will be offered participation if they are being offered skull-based surgery as part of their standard treatment. These are patients that would be recommended skull-based surgery despite this investigation and this investigation will have no influence on treatment recommendations. Consenting and eligible participants will be scheduled for standard of care surgery.

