**Distortion Product Otoacoustic Emissions (DPOAE)**: DPOAEs are a measure of outer hair cell function and will be used as an indicator of changes in cochlear health and possible PTS in the early period following noise exposure. A soft earphone will be inserted into the participant's ear and a series of tones at a comfortable volume will be played at varying frequencies. No participation is required of the participant as DPOAE are an objective assessment of cochlear health. The measurement system will record the level of the emissions evoked by two primary tones, f1 and f2 (f2/f1 = 1.22) at levels 65 and 55 dB SPL respectively. The f2 primary tone

will be swept from 1-6 kHz, and will be repeated at least five times per session in order to calculate the stability of the emission at each session. All data will be identified and stored on a password protected computer. DPOAE recording will take about 20 minutes to complete.

Audiometry: Audiogram will be performed to look for PTS. Earphones will be placed over the participant's ear and a series of tones at a soft volume will be played at varying frequencies, and the participants have to indicate that they hear the tones by pressing a button. Thresholds will be measured from 250 Hz to 16 kHz. If there is an absence of a threshold at the limits of the equipment, the threshold will be reported as equipment limits (in dB HL) + 10 dB HL. As with the DPOAE, all equipment and procedures are based on a clinically approved protocol.

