3.3 Secondary efficacy outcomes

The secondary outcome measures are key audiological and clinical assessments of hearing loss as listed below as continuous level variables.

- DPOAE: Distortion product otoacoustic emissions will be measured at baseline (before surgery), as well as within 8 hours and at 30 days (+/- 3 days) post-surgery to measure both temporary and permanent change in DPOAE amplitude relative to baseline. A change is noted in DPOAE amplitude at any frequency that is significantly greater than the stability of each measurement (i.e., 95% confidence interval of each measurement do not overlap).
- ECochG: Electrocochleography will be measured at baseline (before surgery) and at 30 days (+/- 3 days) post-surgery to measure change in ECochG AP amplitude, latency, and width.
- WIN testing: The Words in Noise Test will be administered at baseline (before surgery) and at 30 days (+/- 3 days) after surgery. The respective scores will be converted to Z-scores to evaluate any change in scores relative to baseline.

The study will also include an exploratory analysis aiming to identify biomarkers of response to ZNS.

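### The DPOAE shift rule has no direction and uses a within-session confidence interval, so amplitude rises and session-to-session variation can count as temporary cochlear change

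*Protocol*

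**What the plan says.** Protocol 4.0 lists the rate of temporary cochlear change as its second secondary efficacy outcome. The criterion is "a DPOAE amplitude shift at any frequency that is significantly greater than the stability of each measurement", explained in brackets as "95% confidence interval of each measurement do not overlap". It is then made into a binary outcome: "The rate of DPOAE shift is the ratio of DPOAE shift-positive subjects to total subjects within each arm". Both PTS definitions in the same section are directional, since each requires an increase in hearing threshold.

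SAP 3.3 carries the same criterion, again unsigned: "A change is noted in DPOAE amplitude at any frequency that is significantly greater than the stability of each measurement". It applies to the measurement within 8 hours of surgery and to the one at 30 days, each relative to baseline.

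The interval comes from Protocol 5.1, where the f2 sweep "will be repeated at least five times per session in order to calculate the stability of the emission at each session". Baseline may be up to 33 days before surgery (30 days plus 3), and the early follow-up is in the recovery area (Protocol 5.5).

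Note (a) of Protocol 3.2 sets who enters the DPOAE analysis: "participants will be excluded if their DPOAE is absent at more than 4/10 frequencies". A present response must exceed the noise floor by more than 5 dB SPL and be "replicable within ±5 dB SPL".

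Protocol 12.2.2 and SAP 7.1.2 analyse DPOAE as a continuous variable by ANCOVA. The table index in SAP 12.1 lists DPOAE amplitude and noise floor, but no shift-positive rate.

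**The concern.** There are three gaps in the rule.

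- **Direction.** Non-overlap of two intervals is symmetric. The secondary objective in Protocol 2.2 is to prevent temporary changes in cochlear health, so a subject whose emission grows should not count as a treatment failure. As written, that subject does.
- **Source of the interval.** Repeats within one session measure how steady the emission is in that session. The rule compares two sessions, on different days and partly in different settings. Whatever varies between sessions enters the difference but not the intervals.
- **Frequencies covered.** A subject with up to 4 of 10 emissions absent stays in the analysis, and the rule does not say that those frequencies are left out.

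At stake is whether the shift rate can separate the arms. If many unchanged ears are called positive, a real difference is diluted and a null result is hard to interpret.

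**Working it through.** **Plan's own figure.** The documents state no error rate, power or sample size for the DPOAE shift rate, so there is nothing to reproduce for this outcome.

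**Inputs from the documents.** Five repeats per session (the stated minimum, Protocol 5.1), 10 frequencies (the denominator in Protocol 3.2(a)), and positive if the 95% CIs separate at any frequency (Protocol 4.0).

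**Assumptions.** Within-session SD *s*, between-session SD, correlation of session effects across frequencies, and t-based CIs. The documents give none of these.

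**Step 1: when two intervals separate.** With equal *s* and 5 repeats, the t quantile on 4 df is 2.776. The CIs separate at a difference of 2 × 2.776 × *s* / √5 = 2.48 *s*. That is about 2.5 dB if *s* = 1 dB and about 5 dB if *s* = 2 dB.

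**Step 2: subjects called positive with no true change.** Monte Carlo, 100,000 subjects per setting:

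| Between-session SD (multiple of *s*) | Correlation across frequencies | Positive | Decreases only counted | Positive through increases only |
|---|---|---|---|---|
| 0 | – | 5.2% | 2.7% | 2.5% |
| 0.5 | 0 | 30% | 16% | 14% |
| 0.5 | 0.5 | 28% | 14% | 14% |
| 1 | 0 | 82% | 57% | 26% |
| 1 | 0.5 | 74% | 40% | 34% |
| 2 | 0 | 99.6% | 91% | 8% |
| 2 | 0.5 | 99% | 66% | 32% |

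The first row shows that testing 10 frequencies is not the main problem: 0.53% per frequency gives about 5% per subject. The excess comes from the omitted session variation.

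**Step 3: other plausible settings.**
- Correlation 0.9, both SDs 1 dB: about 55% positive.
- Within-session SD 1.8 dB, which follows if ±5 dB is read as a 95% limit for the difference of two repeats (5 / (1.96 × √2) = 1.80): 11% to 37% at between-session SD 0.5 to 1 dB, and 61% to 89% at 2 dB.
- Six frequencies instead of 10, independent: 3.2%, 19.6%, 64.5% and 96.6% at multiples 0, 0.5, 1 and 2.
- Ten repeats instead of five, multiple 0.5: 61% to 68%. More repeats tighten the interval around the session mean and make the problem worse.
- Multiplier 1.96 in place of t, no session variation: about 25%. The documents do not say which is meant.

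**Step 4: what dilution does.** As an illustration only, borrow the primary endpoint's design: 50% versus 25%, 78 per arm, one-sided 0.0125. Exact Fisher power is 80.7% (the plan states 80.4%). Suppose 40% of true non-shifters are called positive and all true shifters are detected. The rates become 0.50 + 0.50 × 0.40 = 70% and 0.25 + 0.75 × 0.40 = 55%, and power falls to 32.4%.

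**The case against.** The strongest reply is that the size is assumed. The documents contain no within-session SD, no between-session SD and nothing on probe refitting, and the result runs from 5% to over 99% as those numbers vary. One probe fit may serve a whole sweep, so session effects are probably shared across frequencies, which lowers the rate. This stands: the size can be given only as a range. The mechanism does not depend on it, because the text itself sets a within-session interval against a between-session difference.

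The second reply is that the planned DPOAE analysis is a baseline-adjusted ANCOVA and that no table of the rate is listed. This also stands, and it limits the consequence. Protocol 4.0 nevertheless names the rate as an efficacy outcome.

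A reader might infer more than the documents support:

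- **That the rule contradicts the ±5 dB tolerance in Protocol 3.2(a).** It does not. That tolerance defines a present response. The shift rule compares session estimates built from at least five repeats, which is a different quantity for a different purpose.
- **That the rate must sit near its ceiling in every arm.** This holds only under the larger assumed session SDs.
- **That the plan rules out reseating the probe, or compares noise floors where emissions are absent.** The text is silent on both. The gap is that the rule sets no limit, not that it prescribes the wrong one.
- **That the rule favours zonisamide.** Under blinding the misclassification is the same in all arms, so it dilutes.

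**Conclusion.** The concern holds for the binary shift rate. Its wording has no direction and no restriction to emissions present at baseline, and its interval leaves out between-session variation. With no true change and no session variation, about 5% of subjects are positive, half through increases only. Over the assumed range (within-session SD 1 to 1.8 dB, between-session SD 0.5 to 1 dB, correlation 0 to 0.9) the rate is about 11% to 82%, and it is higher at 2 dB. These figures rest on t-based CIs, 5 repeats and 10 frequencies.

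The effect is loss of sensitivity in one secondary rate. The primary endpoint and the continuous DPOAE ANCOVA are untouched, and temporary change remains testable through the latter.

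**What to change.** Reword Protocol 4.0 and SAP 3.3 so that a subject is shift-positive only if, at one or more f2 frequencies with a present emission at baseline (the 3.2(a) criterion), amplitude decreases so that the post-operative upper 95% limit lies below the baseline lower 95% limit. State that the CI reflects within-session stability only, and whether it is t-based. Add, as a sensitivity analysis, the rate of decreases greater than 5 dB SPL.

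The cost is wording in two sections and a little more analysis work. The sign removes about half of the false positives or less (82% to 57%, or 74% to 40%, when the two SDs are equal), so it does not cure the omitted session variation. The sensitivity analysis addresses that part. With no true change, *s* = 1 dB and independent frequencies, the chance of any decrease above 5 dB is 1 − (1 − Φ(−5/SD_diff))^10, where SD_diff = √(2 × between² + 2 × *s*²/5). This gives about 0.6%, 11% and 35% at between-session SD 1, 1.5 and 2 dB.

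The 5 dB floor should not become the main rule. With *s* = 1 dB, between-session SD 0.5 to 1 dB and correlation 0.5, a true 4 dB fall at three frequencies is flagged in 34% to 49% of subjects with the floor, against 98% to 100% with downward separation alone (partly false positives at 1 dB). Nor should the probe procedure change mid-trial: that would mix baseline methods, and reseating within a session would not capture the difference between clinic and recovery area.

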#### 5.0 SCHEDULED ASSESSMENTS

## 5.1 Screening/Baseline/Preoperative Assessment

The screening and baseline assessments will occur within 30 days (+3 days) of surgery and include the following tests or procedures:

- 1. Documentation of demographic information, including gender, age, allergies, current medications, imaging related to surgery, and planned surgical approach.
- 2. Clinical examination of the ears.
- 3. Documentation of key clinical data such as confirmation of air conduction thresholds in the non-operated ears to be no worse than 25 dB HL for pure tone average 0.5, 1, and 2 kHz with no individual threshold greater than 30 dB HL, and no worse than 45 dB HL at 4 kHz and absence of ear disorder in the ear contralateral to surgery.
- 4. Collection of laboratory test results that include a pregnancy test\*, electrolyte panel, BUN, Cr, ALT, and AST.

  If these tests are not performed as part of pre-operative workup, we will obtain them for research purposes.
  - \*Women capable of becoming pregnant will be asked to have a pregnancy test before beginning this study. If a pregnancy test (urine or serum) is performed as part of pre-operative testing we will collect the results from the medical record for research purposes. Women capable of becoming pregnant will be instructed to use effective birth control methods and not to become pregnant while participating in this study as there may be unknown risks to the unborn child. There may be long-term effects of the treatment being studied that could increase the risk of harm to an unborn child. The study team must be notified if the birth control method fails while on the study and/or if the participant becomes pregnant while participating in this research study.
- 5. Blood sample will be collected for PGx surveys.
- 6. DPOAE, Audiogram, electrocochleography (ECochG), and WIN testing to document the measurements of the non-operated ear.

**Distortion Product Otoacoustic Emissions (DPOAE)**: DPOAEs are a measure of outer hair cell function and will be used as an indicator of changes in cochlear health and possible PTS in the early period following noise exposure. A soft earphone will be inserted into the participant's ear and a series of tones at a comfortable volume will be played at varying frequencies. No participation is required of the participant as DPOAE are an objective assessment of cochlear health. The measurement system will record the level of the emissions evoked by two primary tones, f1 and f2 (f2/f1 = 1.22) at levels 65 and 55 dB SPL respectively. The f2 primary tone

will be swept from 1-6 kHz, and will be repeated at least five times per session in order to calculate the stability of the emission at each session. All data will be identified and stored on a password protected computer. DPOAE recording will take about 20 minutes to complete.

Audiometry: Audiogram will be performed to look for PTS. Earphones will be placed over the participant's ear and a series of tones at a soft volume will be played at varying frequencies, and the participants have to indicate that they hear the tones by pressing a button. Thresholds will be measured from 250 Hz to 16 kHz. If there is an absence of a threshold at the limits of the equipment, the threshold will be reported as equipment limits (in dB HL) + 10 dB HL. As with the DPOAE, all equipment and procedures are based on a clinically approved protocol.

Electrocochleography (ECochG): An ECochG is an electrophysiological measurement of the cochlea in response to sound and it will be used to identify synaptopathy. It is a clinically-approved auditory evoked potential that is used to evaluate the status of the both the cochlear and the auditory nerve fiber. This measurement is obtained by inserting a soft gold-foiled earphone into the participant's ear. This earphone serves to deliver a series of clicks, as well as an electrode to measure the electrophysiological response of the cochlea to the sound. The electrode montage is completed with a ground electrode on the forehead at midline and a gold-foil electrode in the contralateral to serve as the inverting electrode. The impedance between electrodes will be < 3 kΩ for all participants. The click stimuli at 90 dB nHL used for the study will be repeated 2000 times so that the recording signal can be averaged with artifact rejection. The measurement will be repeated three times. Testing time 45 min to 1 hour.

Words in Noise Test (WIN): Earphones will be placed over the participant's test ear and the WIN test will presented to the test ear. The WIN test battery consists of 35 words that are presented with varying degrees of signal-to-noise ratios (SNR) from 24 dB HL to 0 dB HL. The SNR at 24 dB HL is the easiest, with words presented at 24 dB above the babble background, whereas the SNR of 0 dB is the most difficult due to the target words being presented at the same level as the background noise (Wilson and Burks, 2005; Wilson and Watts, 2012). The WIN list will be presented to the test ear one time. The total number of words correctly identified will be used to calculate a dB HL S/N threshold by the Spearman-Karber equation at the mean of 50% correct points. All of speech testing will take 5-10 minutes to complete.

7. Completion of the Hearing History and Occupation Exposure questionnaire and LENS-Q Adapted for Surgical Noise Study.

